## 7 Subject Selection

### 7.1 Study Population and Eligibility

Eligibility for study enrollment is determined by specific eligibility criteria as described in Table 7-1 and Table 7-2.

### 7.2 Inclusion Criteria

Subjects who meet all of the following inclusion criteria (Table 7-1) may be given consideration for enrollment in this clinical study, provided no exclusion criterion (Table 7-2) is met.

**Table 7-1: Inclusion Criteria**

Inclusion Criteria	
 
• Subject is age 18 or above, or of legal age to give informed consent specific to each country and national laws
 
• Subject has a documented diagnosis of heart failure
 
• Subject has a Boston Scientific CRT-D or ICD device implant that has HeartLogic, with Heart Failure Sensors turned ON, Respiratory Sensor turned ON, and Sleep Incline Sensor turned ON
 
• Subject has an active bipolar RV lead implant.
 
• Subject is enrolled in LATITUDE (NXT 5.0 or future version), and is willing to be remotely monitored from the baseline visit for approximately 12 months with HeartLogic disabled
 

---------------------------	--

### 7.3 Exclusion Criteria

Subjects who meet any of the following criteria (Table 7-2) cannot be included in this study or will be excluded from this clinical study.

**Table 7-2: Exclusion Criteria**

Exclusion Criteria	
 
• Subject has received or is scheduled to receive a heart transplant or ventricular assist device (VAD)
 
• Subject is enrolled in any concurrent clinical study without prior Boston Scientific written approval (excluding registries)
 
• Subject has a life expectancy of less than 12 months
 
• Subject has a history of non-compliance to medical care or known inability to comply with requirements of the clinical study protocol
 

---------------------------	--

## 8 Subject Accountability

### 8.1 Point of Enrollment

Subjects are considered enrolled at the point when they sign and date the informed consent form. The consent may be obtained at any point in time following the calendar day of implantation of the device. There is no limitation on the time from post-implantation to consent. However, the baseline visit must occur within 30 days of consent. The eligibility criteria must be confirmed prior to consenting the patient.

## **8.2 Withdrawal**

All subjects enrolled in the clinical study (including those withdrawn from the clinical study or lost to follow-up) shall be accounted for and documented. If a subject withdraws from the clinical study, an “End of Study” eCRF must be completed, with the subject status as “withdrawn”.

Subjects will be classified as “withdrawn” if at least one of the following conditions are met:

- subject lost to follow-up (Section 8.3)
- subject classification of ineligible or attempt (Section 8.4)
- clinician recommendation
- subject choice
- device explant, device revision, or lead revision

All applicable eCRFs up to the point of withdrawal (including the Final Clinic Visit if possible) and the “End of Study” eCRF must be completed.

After a subject has been withdrawn from the study, additional study data will no longer be collected after the point of withdrawal. All open adverse events should be closed or documented as chronic. Data collected up to the point of subject withdrawal may be used for analysis.

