**Figure 2: LATITUDE NXT 5.0 System**

The primary means of device data collection for the PREEMPT-HF study is through the LATITUDE patient management system. Therefore, LATITUDE enrollment is required for subject participation in the study, and data transmission via LATITUDE (i.e., referred to as “monitored on LATITUDE”) must be confirmed at the baseline visit. During the course of the study if the subject is away from the communicator, sensor data storage to PG memory will continue; however, the next data upload will not occur until the subject is within range of the communicator. To ensure timely data transmission, LATITUDE must be programmed for scheduled follow-ups to occur every 3 months or sooner. At the final study visit, the investigational site must interrogate the subject’s device using the PRM. This will trigger a remote data upload to LATITUDE when the subject returns within range of the communicator.

For the PREEMPT-HF study, Heart Failure Sensors must be turned ON. This must be done via the PRM. The Heart Failure Sensors consists of heart sounds (S3 and S3/S1), respiration (respiratory rate and rapid shallow breathing index), impedance, heart rate and activity.

Only subjects with Heart Failure Sensors turned On, Respiratory Sensor turned ON, and HeartLogic disabled are eligible to participate in the study. The state where HeartLogic is **not** enabled on LATITUDE is referred to as HeartLogic disabled. In this state, the device will continue to collect sensor data, but the HeartLogic Index and Heart Sounds sensor trends will not be displayed on the LATITUDE system, and clinicians will not receive HeartLogic alerts. Sensor data will be stored in the PG for 365 days after which the earliest data are overwritten. The subject must be withdrawn from the study if Heart Failure Sensors will be turned OFF, or if HeartLogic will be enabled. Subjects may remain in the study if the Respiratory Sensor or Sleep Incline Sensor are turned OFF; however, this will be considered as a protocol deviation. The Sleep Incline Sensor measures the subject’s average elevation angle over the programmed sleep schedule. Sleep schedule can be programmed using the PRM.

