### 5.1 Primary Objective

The primary objective of the PREEMPT-HF study is to investigate the association between HF Sensor data and 30-day HF readmissions.

Subjects will be followed for approximately 12 months to collect the required number of clinical events to support the study objectives. These events are called Reviewable Clinical Events (RCEs), and include all-cause hospitalizations and HF outpatient visits (as defined below).

[figure not shown]
RCEs require the investigational site to review the subject's medical records and complete the appropriate eCRF (Figure 3).

Clinical events for the purposes of data analysis are defined as follows:

- **Hospitalization (all-cause):** the subject is admitted to inpatient hospital care and discharged on a different calendar date.
- **HF Hospitalization:** the subject is admitted with signs/symptoms of congestive heart failure (CHF) and receives unscheduled augmented HF therapy with oral or intravenous medications, ultrafiltration therapy or other parenteral therapy.
- **HF Readmission (30-day):** the subject is admitted for an unplanned hospitalization for any cause within 30 days post discharge from a HF hospitalization.
- **HF Outpatient Visit:** the subject has signs/symptoms of congestive HF, and receives unscheduled intravenous decongestive therapy (e.g., IV diuretics, IV inotropes, IV vasoactive drugs, ultrafiltration), in a setting that does not involve a hospitalization (e.g.: emergency room, HF clinic, primary care clinic, etc.).

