### 9.10 Study Completion

An “End of Study” eCRF must be completed when the subject’s participation concludes for one of the following reasons:

- The subject completes the final in-clinic visit after 350 days (minimum final clinic visit window). At this point, the subject will exit the study, and device settings can be configured per clinician discretion. The subject status will be “completed study.”
- The subject withdraws from the study. At this point, the subject will exit the study, and device settings can be configured per clinician discretion, and the subject status will be “withdrawn”. All applicable eCRFs (including the Final Clinic Visit if possible) and the “End of Study” eCRF must be completed with information up to the point of withdrawal. Complete a review of the medical records for RCEs to the point of withdrawal, and interrogate the PG (See section 9.9 for visit details). PG interrogation ensures that the device data will be uploaded when the patient returns to within range of the communicator.
- The study is terminated by Boston Scientific. At this point, the subject will exit the study, and device settings can be configured per clinician discretion. The subject status will be “withdrawn.”

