#### 10.1.2 Sample Size

Approximately 3750 enrollments will be required for this study. The sample size was determined based on the estimated number of HF index hospitalizations and 30-day HF readmissions needed to evaluate the primary objective. Final sample size will be determined by an interim analysis as described in Section 10.9. An index HF hospitalization refers to the first HF hospitalization during the study follow-up period. A HF hospitalization is deemed usable if sensor data is available during the event and sufficient follow up time is recorded to determine if a readmission occurs.

A total of 215 usable index HF hospitalizations are required to have at least 80% power to detect a standardized difference of 0.5 in the mean sensor change (admission – discharge) between the groups with and without a 30-day HF readmission. It is expected that of the 215 index HF hospitalizations, 43 will be followed by a 30-day readmission (20%).

A total of 215 usable index HF hospitalizations was determined based on the following assumptions:

- 80% Power to detect a standardized mean difference of 0.5 between groups
- Two-sided type I error (alpha) of 0.05
- 3:1 ratio of group sizes (no-readmission : 30-day HF readmission), where the no-readmission group will exclude index HF hospitalizations with 31 to 60-day readmissions

Assuming a 20% loss of usable HF events due to proximity to study start and exit (completion or withdrawal), a total of 270 index HF hospitalizations are required to obtain 215 usable HF hospitalizations.

Approximately 3750 enrollments are required to obtain the 270 required index HF hospitalizations. This was determined based on the following assumptions:

- 9 % index HF hospitalization rate per patient year
- 20% death/withdrawal rate throughout duration of study
- Average of 12 months of sensor data per subject

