## **17 Safety Reporting**

### ***17.1 Reportable Events by Investigational Site to Boston Scientific***

It is the responsibility of the Investigator to assess and report to BSC any event which occurs in any of following categories:

- All Serious Adverse Events
- All Device Related Adverse Events
  - Events listed in the arrhythmia logbook, should be reported only if determined to be clinical significant by the investigator and/or delegated site staff (e.g.: ATR, PMT, etc.)
  - All arrhythmias which received inappropriate shock therapy as identified by a study investigator must be reported
- All Serious Adverse Device Events
  - Serious adverse device events that are a result of implant, device revision, lead revision, or device/lead explant are not reportable events per this protocol. Patients that undergo device or lead revision/explant must be withdrawn prior to the procedure.
- All Device Deficiencies related to the pulse generator

- Unanticipated Adverse Device Effects/Unanticipated Serious Adverse Device Effects
- HF Related Adverse Events: An adverse event is deemed as a HF Adverse Event if the primary cause is HF and either of following conditions is met:
  - Subject is admitted and discharged with a calendar date change.
  - Subject is not hospitalized but received one or more IV medications including diuretics, inotropes, vasodilators, other parenteral therapy, or aquapheresis.

For event reporting the medical diagnosis must be reported. In case the diagnosis is not available, individual symptoms can be reported to fulfill reporting timelines. If a diagnosis becomes available at a later stage, it must be added to the reported event.

If it is unclear whether or not an event fits one of the above categories, or if the event cannot be isolated from the device or procedure, it should be submitted as an adverse event and/or device deficiency.

Any AE event required by the protocol, experienced by the study subject after informed consent and once considered enrolled in the study (as defined in study subject classification section), whether during or subsequent to the procedure, must be recorded in the eCRF.

Underlying diseases are not reported as AEs unless there is an increase in severity or frequency during the course of the investigation. Death should not be recorded as an AE, but should only be reflected as an outcome of one (1) specific SAE (see Table 17-1 for AE definitions).

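### Stopping all event review at withdrawal makes some completed index HF hospitalizations unusable and does so selectively, although their readmission status could often be completed from medical records

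*Protocol*

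**What the plan says.** Protocol 8.2 lists five grounds for withdrawal: loss to follow-up, classification as ineligible or attempt, clinician recommendation, subject choice, and "device explant, device revision, or lead revision". The consequence is the same for all five: "After a subject has been withdrawn from the study, additional study data will no longer be collected after the point of withdrawal". Data gathered before that point may still be analysed.

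Protocol 17.1 fixes the timing for hardware changes: "Patients that undergo device or lead revision/explant must be withdrawn prior to the procedure". Protocol 4.2 adds two compulsory triggers that do not appear in the 8.2 list: "The subject must be withdrawn from the study if Heart Failure Sensors will be turned OFF, or if HeartLogic will be enabled". Protocol 9.10 asks for a closing check, but only up to the same date: "Complete a review of the medical records for RCEs to the point of withdrawal, and interrogate the PG".

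Under Protocol 10.1.2 an index event is usable only if sensor data exist for the event and "sufficient follow up time is recorded to determine if a readmission occurs". The outcome in Protocol 5.1 is that "the subject is admitted for an unplanned hospitalization for any cause within 30 days post discharge from a HF hospitalization". Protocol 10.1.3 also removes subjects with an HF hospitalization on days 31 to 60, so a subject belongs to the no-readmission group only once 60 days are known.

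**The concern.** Withdrawn consent and a hardware change are different things. Withdrawn consent ends the right to look at records. A hardware change ends or alters the sensor stream but leaves the medical record open. The plan treats them alike.

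For a subject already discharged from the index HF hospitalization, the sensor change from admission to discharge has been measured. What is missing is readmission status, which sites already establish at the interim review from records alone (Protocol 9.8). If that review stops early, a completed index event is discarded.

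The primary analysis compares mean sensor change between the two groups. Events lost at random would cost only precision. If the lost subjects differ in sensor change from those kept in their group, the comparison shifts as well.

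**Working it through.** **1. What happens to one index event, by sequence**

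- Discharge, readmission and completed stay, then withdrawal: the readmission falls within the closing review (9.10) and the event is classifiable.
- Discharge, then withdrawal before day 30 with no readmission yet: status unknown, event unusable under 10.1.2.
- Discharge, then withdrawal between days 31 and 60 with no readmission yet: 30-day status is known, but the exclusion in 10.1.3 cannot be applied.
- Discharge, then an unplanned readmission that leads to a revision: 17.1 puts withdrawal before the procedure. Protocol 5.1 defines a hospitalization by discharge on a later calendar date. The admission is visible to the closing review, but the discharge may fall after collection has stopped.
- Withdrawal before any index event: records cannot help, because sensor data with HeartLogic disabled are needed.

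**2. The plan's own figures (Protocol 10.1.2)**

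- Inputs: standardized difference 0.5, two-sided alpha 0.05, ratio 3:1, 20% readmitted, 20% loss of usable events, 9% index rate per patient-year, 20% death/withdrawal.
- Noncentral t power for 43 against 129 is 0.806 (42 against 126 gives 0.797). 43 + 129 = 172.
- 172/0.80 = 43/0.20 = 215. The remaining 215 - 172 = 43 would be the excluded 31-60-day group; that split is inferred.
- 215/(1 - 0.20) = 268.75, so 269 (stated 270).
- 270/(0.09 x 0.80) = 3750.

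The chain reproduces.

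**3. How many index events could be cut off**

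The protocol does not split withdrawals by reason, so only a range under assumptions is possible. Assumptions:

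- Index events are uniform over 365 days.
- The 20% is read as a 12-month risk with constant hazard h = -ln(0.80) = 0.223 per year.
- m multiplies that hazard after an HF discharge.
- Losses near study start are left out.

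Formulas: the share cut off by death or withdrawal within w days is 1 - exp(-h x m x w/365). Scheduled exit removes w/365. Total loss is 1 - (1 - w/365)(1 - share cut off).

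For w = 30 (scheduled exit 30/365 = 8.2%):

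- m = 1: 1.8%, 4.9 of 270; total loss 9.9%
- m = 3: 5.4%, 14.5 of 270; total loss 13.1%
- m = 5: 8.8%, 23.7 of 270; total loss 16.3%

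For w = 60 (scheduled exit 60/365 = 16.4%):

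- m = 1: 3.6%, 9.7 of 270; total loss 19.4%, 217.5 usable
- m = 2: 7.1%, 19.1 of 270; total loss 22.3%, 209.7 usable
- m = 3: 10.4%, 28.1 of 270; total loss 25.1%, 202.1 usable
- m = 5: 16.8%, 45.2 of 270; total loss 30.4%, 187.8 usable

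At each m these are upper bounds for this point, because they include deaths and every withdrawal reason.

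Power with 20% of usable events readmitted and 60% in the no-readmission group: 0.806 at 215 usable, 0.787 at 205, 0.766 at 195, 0.744 at 185.

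**4. Selectivity**

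Suppose only subjects who would never have been readmitted are lost, with loss fraction x among them. The observed readmission share is then 0.20/(0.20 + 0.80(1 - x)):

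- x = 3.6%: 20.6%
- x = 10%: 21.7%
- x = 17%: 23.1%

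If some of those lost would have been readmitted after withdrawal, readmissions are lost too and the share moves back. The documents do not settle which dominates.

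**The case against.** The strongest reply is that the plan expects this loss. Protocol 10.1.2 allows for 20% unusable events and names withdrawal as a cause. At the plan's own average rate, scheduled exit plus withdrawal comes to 19.4% on a 60-day window. Protocol 10.9 checks the withdrawal rate at an interim analysis. The study is exploratory, with no formal hypotheses (10.1.1). All of this stands as far as the number of events goes. It does not address which events are lost.

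A second reply is that ending follow-up when HeartLogic is enabled is deliberate: Protocol 6.4 requires that subjects are not managed with the feature and that clinicians are blinded to it. This stands, and such events should not enter the main comparison.

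A third is that the sensor data may be incomplete. The synopsis describes trends before admission and after discharge, and upload after interrogation waits until the subject is near the communicator (4.2). This also stands: records complete an event only where its sensor data were retrieved.

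Stronger readings are tempting, but the documents do not support them:

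- **That the rule thins the readmission group by a calculable number.** Readmissions completed before withdrawal still count, and no reason-specific rates are given.
- **That these withdrawals are tied to worsening HF.** This is plausible, but nothing in the protocol says so.
- **That collection stops without any closing step.** A records review, an interrogation and, if possible, a final visit are required at withdrawal.

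**Conclusion.** The point holds for index HF hospitalizations that ended before withdrawal and whose sensor data were retrieved. For these, Protocol 8.2, 9.10 and 17.1 together discard events whose readmission status could be completed from records, and keep or lose them according to whether a readmission came first. A readmission that leads to a revision may also be cut off before its discharge date.

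Size and net direction are unknown. Under the stated assumptions, at most 9.7 of 270 events are cut off within 60 days at average hazard and 28.1 at three times that hazard, counting deaths and all reasons. The 20% allowance holds at average hazard and is exceeded at twice it (22.3%). It offers no protection against selective loss at any rate.

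This is a worthwhile, inexpensive improvement to an exploratory comparison that expects 43 readmissions. It is not a flaw that undermines the sample size.

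**What to change.** - In 8.2 and 9.10, for withdrawals other than subject choice, ineligible/attempt or lost to follow-up, stop sensor data at the withdrawal date. Continue records-only review for RCEs, including discharge dates, until 60 days after any HF discharge that preceded withdrawal, where consent permits.
- Report withdrawals by reason and by time since the last HF discharge.
- Where HeartLogic is enabled within that window, keep the event out of the main comparison, as 6.4 requires, and use it only in a flagged sensitivity analysis.
- Reconcile the 4.2 triggers with the 8.2 list, so that these exits have a category of their own.

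No withdrawal trigger or clinical rule changes. The cost is amendment wording, a check or change of the consent text, and one extra record review for a few subjects. Some readmissions counted this way will follow a device change, so that circumstance should be recorded with the event.

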## **8.3 Lost to Follow-Up**

A subject will be considered lost to follow-up if he or she fails to return for the final clinic visit and is unable to be contacted by the study site staff.

The following actions need to be taken if a subject fails to return to the clinic for the final clinic visit:

- The site will attempt to contact the subject and reschedule the missed visit and ascertain if the subject wishes to continue in the study.
- Before a subject is deemed lost to follow-up, the investigator or designee will make every effort to regain contact with the subject (3 documented attempts with a minimum of one certified letter sent to the subject). These contact attempts should be documented in the subject’s medical record or study file.
- Should the subject continue to be unreachable, he or she must be withdrawn from the study with a primary reason of lost to follow-up.

## **8.4 Subject Status and Classification**

Subjects will be classified as follows:

- Consent ineligible
  - Refers to a subject that signs the Informed Consent but does not meet eligibility criteria

- Attempt
  - Refers to a subject that signs the Informed Consent and meets the eligibility criteria, but does NOT meet AT LEAST ONE of the conditions below:
    - Subject is monitored on LATITUDE as of the baseline visit
    - HeartLogic is disabled in LATITUDE as of the baseline visit
    - The frequency of scheduled remote follow-ups in the LATITUDE system is 3 months or less
- Monitored on LATITUDE
  - Refers to a subject that signs the Informed Consent, meets the eligibility criteria, and meets ALL the conditions below:
    - Subject is monitored on LATITUDE as of the baseline visit
    - HeartLogic is disabled in LATITUDE as of the baseline visit
    - The frequency of scheduled remote follow-ups in the LATITUDE system is 3 months or less

### ***8.5 End-of-Study Definition***

The PREEMPT-HF study is considered completed when participants are no longer being actively followed and/or the last participant's final clinic visit has occurred.

## **9 Study Methods**

### ***9.1 Data Collection***

The details of the data collection and the study follow up schedule are shown in Table 9-1. All required data elements must be entered into the PREEMPT-HF study eCRFs.

